# **Analysis of Primary Endpoints**

# 8.8.1. Primary Endpoints

Degradation of the SBP over seven days as measured by the Corneometer®.

The breakdown of the SBPs on the volar forearm test areas will reflect the duration of wear of the SBPs. Independent sample t-tests or non-parametric equivalent tests will be used to compare mean Marathon® and Cavilon™ Corneometer® values at baseline (Visit 1), Visit 2, Visit 3, Visit 4, Visit 5, and the final Visit 6 for untreated control area and volar forearm test area measurements. Paired-sample t-tests will be used to compare any two data points for a given SBP and location.

The breakdown of the SBP on the inner elbow test area, relative to the corresponding volar forearm test area, will reflect the durability of the products. Derived variables will be created to calculate the difference between the volar forearm test area measurement and the inner elbow test area measurement at baseline (Visit 1), Visit 2, Visit 3, Visit 4, Visit 5, and the final Visit 6. Independent sample t-tests or non-parametric equivalent tests will be used to compare mean Marathon® and Cavilon™ Corneometer® difference values at baseline (Visit 1), Visit 2, Visit 3 and the final Visit 6 on Day 8. Paired-sample t-tests will be used to compare any two data difference points for a given SBP.

Both degradation and durability endpoints will be graphed across time by SBP with and without 95% confidence intervals of the mean.

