# 1.2. Schedule of Activities (SOA)

Assessments and Activities#	Pre-visit Activities	Visit 1	Visit 2–5	Visit 6 (Final visit)
Informed consent	X			
Participant Screening	X			
Demographics	X			
Participants complete minimum 18 hours washout period	X			
Participants wash forearms and inner elbows with standardized soap, and dry them using paper towels		X		
Participant forearms and inner elbows allowed to dry		X		
Randomization of SBP to be applied to the dominant arm of the participant §¥		X		
Baseline Corneometer® measurements taken		X		
SBPs applied at the volar forearm and inner elbow test areas according to the Randomization Schedule§		X		
SBPs allowed to dry		X		
Post-application Corneometer® measurements taken at untreated control areas and test areas		X	X	X
Participants complete surveys regarding experience with the SBPs ¥		X	X	X
Monitoring for adverse device events		X	X	X
Participant dismissal				X

# Study activities will occur after informed consent has been signed, and the participant has met all the inclusion criteria and none of the exclusion criteria.

08-AUG-2022

Version 2.0 CONFIDENTIAL Page 10 of 28

§ Randomization will assign each participant to either Marathon® or Cavilon™ (designated SBP). The designated SBP will be applied to the volar forearm and inner elbow test areas of the participants' dominant arm (as determined by the participant), whereas the other SBP will be applied to the volar forearm and inner elbow test areas of the participants' non-dominant arm.

\*The same type of SBP will be applied to the volar forearm and inner elbow test areas.

<sup>£Participants will complete surveys on Visits 1, 3, and 6.

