wrist), and baseline Corneometer® measurements will be taken. Per the Randomization Schedule. each participant will be assigned to either Marathon® or Cavilon™ (designated SBP). The designated SBP will be applied to the volar forearm and inner elbow "test areas" on the participants' dominant arm (as determined by the participant). The other SBP will be applied to the volar forearm and inner elbow "test areas" on the participants' non-dominant arm. A distinct area of each volar forearm of the participants will be used as an "untreated control area" for the test areas on that forearm. To assess baseline skin hydration, study personnel will use the Corneometer® to take the average of five initial measurements of skin capacitance and the standard deviation of the measurements, for each of the untreated control areas and the volar forearm and inner elbow test areas. After the baseline measurements have been recorded, the study personnel will apply the two SBPs, Marathon® and Cavilon™, according to the Randomization Schedule to test areas on the participants' volar forearm and the inner elbow. After the SBPs have been left to dry for at least one minute or have dried completely, Corneometer® measurements will be repeated in the untreated control areas and the volar forearm and inner elbow test areas in a manner similar to the baseline measurements. Thereafter, daily Corneometer® measurements will be taken over a seven-day period with a two-day break over the weekend. During the study period, participants will be allowed to bathe their arms using a standardized soap provided by the study personnel but will be instructed to minimize scrubbing or any other abrasion of the skin of the volar forearms and inner elbows. In addition, participants will be instructed not to engage in activities, for eg, sports (eg, tennis) or holding a baby that may cause significant abrasion on one arm and not the other. On the last day of the study (Visit 6), study personnel will take the last set of Corneometer® measurements. In addition, participants will complete surveys regarding their experience with the two SBPs on specific days during study participation.

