# 6.2.2 Randomization of Target Areas

Study personnel will confirm that the washout period of minimum 18 hours prior to Visit 1, has been successfully completed. Participants will wash their forearms and inner elbows with a standardized soap and use paper towels to dry each arm. After the participants' forearms and inner elbows are fully dried, they will be randomized according to the Randomization Schedule.

Figure 6.2.2. Randomization of Untreated Control Areas and Test Areas on the Volar Forearms and Inner Elbows

[figure not shown]

Figure 6.2.2. Key	
LL	Lower left
UL	Upper Left
LR	Lower Right
UR	Upper Right
LIE	Left Inner Elbow
RIE	Right Inner Elbow

Note: The inner elbow test areas will receive the same SBP as the one applied to the test area of the same arm

Medline Industries, LP

An evaluation of the skin protection characteristics of two commercially available skin barrier protectants MED-2022-DIV71-003

08-AUG-2022

Version 2.0 CONFIDENTIAL Page 17 of 28

Randomization will assign each participant to either Marathon® or Cavilon™ (designated SBP). The designated SBP will be applied to the volar forearm and inner elbow "test areas" of the participant's dominant arm, as determined by the participant. The other SBP will be applied to the volar forearm and inner elbow "test areas" of the participant's non-dominant arm. The SBP applied to the volar forearm and inner elbow test areas of a particular arm will be the same. Randomization will provide an equal probability for an SBP to be assigned to either the dominant or non-dominant arm. A distinct area on a particular volar forearm of the participant will be used as an "untreated control area" for the test areas on the same forearm.

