#### 8. STATISTICAL CONSIDERATIONS

#### 8.1. Sample Size Determination

A sample size of 42 was elected for a superiority margin of at least 15 arbitrary capacitance units  $(A.C.U)^{10}$  as measured by the Corneometer® with an estimated mean of pair differences of 17.5 and the standard deviation of 5.05, given the 80% power at Bonferonni adjusted significance level of  $\alpha = .0125$ . Internal evaluation SBP data was used as a starting point, and PASS- Paired T-Tests for Superiority by a Margin procedure was utilized for the sample size estimation (PASS 2021 Power Analysis and Sample Size Software (2021). NCSS, LLC. Kaysville, Utah, USA, ncss.com/software/pass).

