### 8.8. Statistical Analysis

Statistical analyses will be conducted in SAS® software, Version 9.4 or higher of the SAS System for Windows (Copyright © 2013 SAS Institute Inc.) or other appropriate statistical software. P < .05 will be considered statistically significant.

All continuous variables will be summarized for the full sample and by SBP group using the following descriptive statistics: (non-missing sample size), mean, standard deviation, median, maximum and minimum. The frequency and percentages (based on the non-missing sample size)

Medline Industries, LP
An evaluation of the skin protection characteristics of two commercially available skin barrier protectants
MED-2022-DIV71-003
08-AUG-2022

Version 2.0 CONFIDENTIAL Page 23 of 28

of observed levels will be reported for all categorical measures. 95% confidence intervals will be calculated for all means.

Spearman correlation analysis will be used to examine possible associations between the key variables of Marathon® or Cavilon™ use and the Corneometer® measurements at various timepoints with covariates of age, sex, and dominant arm. Additional t-tests or non-parametric tests will be employed to further examine any significant associations found in the correlational analyses between key and covariate measures.

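### The primary product comparison uses independent-sample tests with no stated margin, although each participant carries both products and n = 42 was sized for a paired test against 15 A.C.U.

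*Combined protocol and SAP*

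**What the plan says.** **Design.** The randomized product goes on the dominant arm. Section 4.1 continues: "The other SBP will be applied to the volar forearm and inner elbow" test areas of the non-dominant arm. The footnote to the Schedule of Activities (1.2) says the same ("whereas the other SBP will be applied to the volar forearm and inner elbow test areas" of the non-dominant arm), as does section 6.2.2. Each person therefore supplies one Marathon and one Cavilon reading per site and visit.

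**Sample size (8.1).** "A sample size of 42 was elected for a superiority margin of at least 15 arbitrary capacitance units", with a mean pair difference of 17.5, an SD of 5.05, 80% power and a Bonferroni-adjusted alpha of .0125. The method is named: "Paired T-Tests for Superiority by a Margin procedure was utilized for the sample size estimation".

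**Analysis (8.8 and 8.8.1).** For the forearm values, and again for the forearm-minus-elbow differences, the two products are compared as follows: "Independent sample t-tests or non-parametric equivalent tests will be used to compare mean" values by product at the listed visits. Paired tests appear only within a product; for durability the text reads "Paired-sample t-tests will be used to compare any two data difference points for a given SBP". Neither section gives a margin or a null value. Section 8.8 sets the threshold: "P < .05 will be considered statistically significant".

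**The concern.** Two faults meet in the only planned between-product test of the primary endpoint.

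First, the independent-sample test assumes that the Marathon and Cavilon readings come from unrelated people. They come from the same people on the same day. If a participant's two arms are correlated, the test uses the wrong standard error, so its p-value and the matching confidence interval for the product difference are wrong. The non-parametric equivalent of an independent-sample test is also unpaired, so the fallback does not help.

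Second, 8.1 powers a claim that one product exceeds the other by more than 15 A.C.U., while 8.8.1 gives no margin. Read in the ordinary way, it tests whether the means differ at all. A significant result would then not show what the 42 participants were recruited to show. Section 8.1 also does not say which endpoint or visit its figures describe, so a reader cannot assign the 80% power to any particular test in 8.8.1.

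**Working it through.** **Inputs from section 8.1:** n = 42 pairs; margin 15; expected mean difference 17.5; SD of pair differences 5.05; alpha .0125; power 80%.

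**Assumptions:**
- The alpha is one-sided. Section 8.1 does not say, but a test of superiority by a margin is directional.
- The between-arm correlation ρ is not given. Values of 0, 0.3, 0.5 and 0.7 are used, with the pair-difference SD held at 5.05.
- The two arms have equal variance.

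**Step 1: reproduce n = 42.** For the paired test against the margin, the noncentrality is (17.5 − 15)/5.05 × √42 = 3.21 on 41 degrees of freedom. Power is .807 at n = 42 and .796 at n = 41, so 42 is the smallest n reaching 80%. Two-sided .0125 would need 49 and gives 72% at 42. The stated n therefore belongs to the paired margin test at one-sided .0125.

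**Step 2: what that test requires.** Paired SE = 5.05/√42 = 0.779. The smallest significant observed mean difference is 15 + t(.9875, 41) × 0.779 = 15 + 2.327 × 0.779 = 16.81 A.C.U. The paired 95% half-width is t(.975, 41) × 0.779 = 2.020 × 0.779 = 1.57 A.C.U.

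**Step 3: the independent test on the same data, null value zero, two-sided .05.** Per-arm SD = 5.05/√(2(1 − ρ)). The SE used by the independent test exceeds the true SE by the factor 1/√(1 − ρ). The significance threshold, which is also the 95% half-width, is t(.975, 82) × 0.779/√(1 − ρ), with t = 1.989. Type I error was obtained by numerical integration over the variances of the within-person sum and difference; simulation agrees.

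| ρ | per-arm SD | SE ratio | threshold / half-width (A.C.U.) | actual type I error | power at a true difference of 3 |
|---|---|---|---|---|---|
| 0 | 3.57 | 1.00 | 1.55 | .050 | 97% |
| 0.3 | 4.27 | 1.20 | 1.85 | .020 | 93% |
| 0.5 | 5.05 | 1.41 | 2.19 | .006 | 85% |
| 0.7 | 6.52 | 1.83 | 2.83 | .001 | 59% |

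The paired test has 96% power at a true difference of 3, an illustrative value. The rank-sum alternative has type I error of about .020, .007 and .001 at ρ = 0.3, 0.5 and 0.7. At the planned difference of 17.5, power against zero is about 100% with either test.

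**Step 4: keep the independent test but restore the 15-unit margin and one-sided .0125.** At n = 42, power is 82%, 68%, 50% and 19% at ρ = 0, 0.3, 0.5 and 0.7, against 81% for the paired test.

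**Step 5: the hypothesis gap.** Without a margin, at ρ = 0.3 to 0.7, an observed difference of about 1.9 to 2.8 A.C.U. is significant. The test in 8.1 needs about 16.8. Even the paired test without a margin reaches p < .05 with 88% probability when the true difference is only 2.5 A.C.U.

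**The case against.** The best case for leaving this alone is that little is lost at the planned effect. If 8.8.1 is a test of equality, power at 17.5 is about 100% whether or not the pairing is used, and with positive correlation the independent test is conservative, so it creates no false claims. The loss appears only at small differences such as 3 A.C.U., a value the plan does not contain, and only for a correlation the plan does not give. At ρ = 0.1 or 0.2 the type I error is about .04 or .03 and power at 3 is nearly unchanged. If instead the margin is meant to carry over, the hypothesis gap closes. Section 8.1 also never states outright that its pairs are Marathon against Cavilon, nor whether its alpha is one-sided. Finally, the SD of 5.05 may not apply to the forearm-minus-elbow contrast, where the correlation may also differ.

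Much of this stands as a limit on size. The pairing error is conservative, its magnitude rests on an assumed ρ, and the A.C.U. figures hold only for a comparison to which the 5.05 applies. It does not remove the fault. The two readings are alternatives, and each leaves a defect: without the margin, a significant result does not address the powered claim; with it, the independent test falls short of 80% power at each of the assumed values 0.3, 0.5 and 0.7. Product pairs are the natural reading of 8.1, given the primary objective and a superiority test, and one-sided .0125 reproduces n = 42 where two-sided .0125 does not. Nothing elsewhere in section 8 plans a paired between-product test.

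**Conclusion.** The concern holds and should be corrected before analysis. That the independence assumption conflicts with the design follows from the text alone and needs no assumed figure. How much it matters depends on the unknown correlation: nothing in efficiency at ρ = 0, and a standard error 20% to 83% too large at ρ = 0.3 to 0.7, always in the conservative direction. The sample size of 42 is right for the test named in 8.1; the fault is that 8.8.1 does not perform that test. The mismatch in hypothesis is conditional on reading 8.8.1 as a test of equality, which is the ordinary reading when no null value is given. On that reading it affects what a significant result means, not the chance of obtaining one at 17.5.

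**What to change.** 1. In both product-comparison paragraphs of 8.8.1, replace the independent-sample tests with a paired t-test, or a Wilcoxon signed-rank test, on the within-participant product difference at each listed visit. Report the confidence interval of that difference.
2. The sponsor should state which endpoint, visit or visits, product direction and alpha (with sidedness) the 8.1 calculation covers. For those comparisons only, test the paired difference against 15 A.C.U. at the 8.1 alpha. Under the 8.1 assumptions this gives 80.7% power with the existing 42 participants. Alternatively, restate 8.1 so that its power describes the test actually used.
3. Do not carry the 15-unit margin over to baseline or to the forearm-minus-elbow contrast without a justification.

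Adjustment for baseline or arm dominance is optional. The first change is a rewording. The second needs a sponsor decision before analysis. Neither needs new data or more participants.

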**Study Description:** 

The skin is the largest organ in the human body serving a myriad of vital functions. In addition to being the organ of touch, heat, and cold, the skin is a physical barrier to microbes and the environment and helps regulate body temperature. There are numerous circumstances in the healthcare environment where supporting the barrier function of the skin is important. For example, skin that is chronically subjected to moisture and chemical stress (eg, fecal and urinary incontinence, high levels of mucus or perspiration) is susceptible to skin breakdown. Treating the affected skin with a barrier would reduce this stress on the skin. Additionally, skin changes naturally with age and elderly patients often have frail skin that can tear easily. Treating the periwound area with a skin barrier protectant (SBP) would shore up the frail skin and limit the extension of the tear. The current study will evaluate the duration of wear and durability of two commercially available SBPs: Medline Marathon® XL No Sting Cyanoacrylate Skin Protectant (henceforth referred to as "Marathon®") and 3M™ Cavilon™ Advanced Skin Protectant (henceforth referred to "CavilonTM"). The presence and deterioration over time of the SBPs will be measured with a Corneometer® CM 825 (henceforth referred to as "Corneometer®"), which is a device that determines skin surface hydration via measurement of skin capacitance. After baseline measurements are taken using the Corneometer®, the volar surface of the forearms (henceforth referred to as "volar forearms") and inner elbows of the participants will be randomized for treatment with the SBPs. A distinct area of each volar forearm of the participants will be left as an untreated control. After the SBPs have dried completely, Corneometer® measurements will be taken again. Thereafter, measurements will be taken daily over a period of seven days with a two-day break over the weekend. The final Corneometer® measurements will be taken on Monday or Tuesday, depending on the date of the participants' first visit (Visit 1). The participants will also complete a survey regarding their experience with the two SBPs on specific days during study participation.

Medline Industries, LP
An evaluation of the skin protection characteristics of two commercially available skin barrier protectants
MED-2022-DIV71-003
08-AUG-2022

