#### 3. OBJECTIVES AND ENDPOINTS

OBJECTIVES	ENDPOINTS	JUSTIFICATION FOR ENDPOINTS
Primary		
To evaluate and compare the duration of wear and durability of Marathon® and Cavilon™	Degradation of the SBPs over seven days as measured by the Corneometer.  1a. The breakdown of the SBPs on the volar forearm will reflect the duration of wear of the SBPs.  1b. The breakdown of the SBPs on the inner elbow, relative to the volar forearm, will reflect the durability of the SBPs.	This endpoint will be an objective measurement of the deterioration of the SBPs, and in turn, the skin protection they offer over time.
Secondary		
To collect information on the participant experience with the two SBPs	Responses to participant surveys	This endpoint evaluates the participants' experience with the SBPs.

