# 6.2.3 Application of Skin Barrier Protectants (SBPs) and Corneometer® Measurements

Study personnel will draw 2-inch x 2-inch squares on the participants' forearms for each untreated control area and each test area using a non-toxic marker, such that three squares are marked on each volar forearm and inner elbow taken together. The lower squares on the volar forearms (LL and LR) will be marked about two inches above each wrist and will be used as untreated control areas. The upper squares on the volar forearms (UL and UR) will be used as test areas. The squares marked on the inner elbows of the participants (LIE and RIE) will be used as test areas as well. Refer to Figure 6.2.2 for details.

To measure baseline skin hydration, study personnel will use the Corneometer® to take the average of five measurements of skin capacitance and the standard deviation of the measurements for both the left and right forearm within each of the untreated control areas and volar forearm and inner elbow test areas. The Corneometer® measurements will be recorded in the CRF.

After the baseline measurements have been taken, study personnel will apply a thin layer of either Marathon ® or Cavilon TM (per the Randomization Schedule), such that the SBP covers the participants' skin within the border of the volar forearm and inner elbow test area squares. Each volar forearm will also include a 2-inch x 2-inch untreated control area square where no SBP will be applied. The participants will not be informed about the type of SBP applied to the volar forearm and inner elbow test areas. The participants will be instructed not to leave the study room, and that their forearms must remain exposed such that no article of clothing comes in contact with their forearms and inner elbows.

After the SBPs have been left to dry for at least one minute or have dried fully, Corneometer® measurements will be repeated in a manner similar to the baseline measurements, for each of the two untreated control areas and four test areas. The average of the Corneometer® measurements and the standard deviation of the measurements will be recorded in the CRF.

Participants will be dismissed from the study room and will be instructed to return the next day (within a  $24 \pm 4$  hours window) for Visit 2.

Medline Industries, LP
An evaluation of the skin protection characteristics of two commercially available skin barrier protectants
MED-2022-DIV71-003
08-AUG-2022

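### The forearm product test for duration of wear compares raw readings and omits the fresh-film reading, so a difference between intact films can be reported as a difference in wear

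*Combined protocol and SAP*

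**What the plan says.** Section 3 defines the primary endpoint as "Degradation of the SBPs over seven days as measured by the" Corneometer, and adds: "The breakdown of the SBPs on the volar forearm will reflect the duration of wear of the SBPs". The notes to section 4.1 give the direction. Treated skin reads lower than untreated skin, and the reading climbs as the film fails.

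Section 6.2.3 fixes the order at Visit 1: "After the baseline measurements have been taken, study personnel will apply a thin layer of either Marathon" or the other product. Baseline is therefore a pre-application reading. After drying, "measurements will be repeated in a manner similar to the baseline measurements" on the two control squares and the four test squares, so a fresh-film reading exists for every participant and product.

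Section 8.8.1 sets out the forearm comparison: "Independent sample t-tests or non-parametric equivalent tests will be used to compare mean Marathon® and Cavilon™ Corneometer® values at baseline (Visit 1"), continuing through "Visit 2, Visit 3, Visit 4, Visit 5, and the final Visit 6 for untreated control area and volar forearm test area measurements". The post-application reading is not listed, and no change from it is formed. For durability, the forearm-minus-elbow difference is derived at baseline and Visits 2 to 6 and tested between products at baseline and Visits 2, 3 and 6, again without the post-application value. The paired tests are within one product.

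Section 8.6 defines a Degradation Rate, (C_o − C_t)/C_o, with interest in when it reaches 50%. C_o is described only as the original measurement, and section 8.8.1 attaches no product test to the rate.

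The drying condition for the post-application reading differs between places. The study description in section 1.1 has "After the SBPs have dried completely". Section 6.2.3 has "After the SBPs have been left to dry for at least one minute or have dried fully", and section 4.1 and the intervention description in the synopsis agree with it.

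**The concern.** Wear is a change: how far the reading has moved from where the intact film put it. The planned forearm test looks only at where the reading stands at a visit. If the two intact films read differently, that gap is carried into every later comparison. It is a property of the products, so assigning them at random to dominant and non-dominant arms balances skin and use but leaves the gap in place. At stake is whether the primary comparison for duration of wear answers the question in section 3, or partly answers a different one, namely which film gives the lower reading.

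**Working it through.** **1. The plan's own figure.** Inputs from section 8.1: mean pair difference 17.5, margin 15, SD 5.05, alpha 0.0125, power 80%. The standardised effect is (17.5 − 15)/5.05 = 0.495. A paired t-test for superiority by a margin, using the noncentral t and one-sided alpha 0.0125, gives n = 42 with power 80.7%. The stated 42 reproduces. (Two-sided 0.0125 would give 49; power at 42 would be 72.2%.) Section 8.1 does not say whether 17.5 and 5.05 describe a raw reading or a change, or at which visit.

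**2. What the raw test measures.** For products A and B at visit t:

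C_t,A − C_t,B = [(C_t,A − C_post,A) − (C_t,B − C_post,B)] + [C_post,A − C_post,B]

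The first bracket is the difference in rise. The second is the fresh-film difference, which the plan neither tests nor removes.

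**3. Illustrations.** Write a reading as U − f × D, where U is the untreated reading, D the drop caused by fresh film and f the share of film effect remaining. All values are assumed, with U = 40 on both arms.

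| Case | Fresh A, B | Later A, B | Raw A − B | Rise A, B | Share lost A, B |
|---|---|---|---|---|---|
| Reversal | 10, 25 | 25, 28 | −3 | 15, 3 | 50%, 20% |
| Equal share lost | 10, 27.5 | 22, 32.5 | −10.5 | 12, 5 | 40%, 40% |
| No reversal | 20, 25 | 30, 26.5 | +3.5 | 10, 1.5 | 50%, 10% |

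In the first row the identity gives (15 − 3) + (10 − 25) = 12 − 15 = −3: the raw test favours A, which wore more on both scales. Reversal requires f_A < f_B together with D_A/D_B > f_B/f_A. In the first row 30/15 = 2 exceeds 0.8/0.5 = 1.6. In the third, 20/15 = 1.33 does not exceed 0.9/0.5 = 1.8.

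**4. How often a gap alone would be declared a difference.** The simulation used 10,000 trials, 42 pairs, equal rise on both arms, the planned independent t-test at two-sided 0.05, a raw pair SD taken as 5.05, and an assumed between-arm correlation of 0 to 0.8. A fresh-film gap of 2.5 units is declared a product difference in 14% to 89% of trials; a gap of 5 units, one third of the 15-unit margin, in 97% to 100%. The lower ends belong to correlation 0.8, where an independent test on paired data loses power.

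**5. The Degradation Rate in section 8.6.** With C_o post-application, film A above gives (10 − 25)/10 = −1.5. The rate falls below zero as film wears and never reaches +50%. With C_o pre-application, it is (40 − 10)/40 = 75% on fresh film and (40 − 25)/40 = 37.5% later, so it measures film effect still present, not loss.

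**6. Durability.** Apply the identity to forearm minus elbow on one arm. The fresh-film term becomes the between-product difference in post-application forearm-minus-elbow values. A product offset equal at both sites cancels. The term survives only if the fresh-film drop differs by site and by product.

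**The case against.** The strongest reply is that the plan does contain change measures. Section 8.6 defines a relative change, the within-product paired tests may take any two time points and so could use the fresh-film reading, and degradation is to be graphed by product with confidence intervals. This stands as evidence of intent, and it means a reader should not infer that the trial can say nothing about wear. It does not cure the test: no between-product comparison uses any of these, and the rate has no defined reference. The control squares do not help either. They are compared separately, and untreated skin carries no information about a film offset.

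Three stronger readings are tempting and are not supported.

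- A reader might infer that a lower-reading film will also look more durable in the protocol's own sense. It need not, because an offset common to forearm and elbow cancels. Natural forearm-elbow differences belong to the skin and are balanced by random assignment of the arms.
- A reader might take the larger rise as proof of more wear. With U = 40, a film going from 10 to 30 and one going from 25 to 35 have lost 20/30 and 10/15, both 67%. Absolute rise depends on the initial drop, as the equal-share row also shows (12 against 5), so it is not a sufficient replacement by itself.
- A reader might infer that the ranking will reverse. Nothing in the documents gives the fresh-film gap, and the third row shows a gap without reversal.

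It is also fair to say that the drying wording is a separate matter of consistency. No effect on readings is shown. It matters here because that reading would become the reference.

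**Conclusion.** The point holds for the forearm comparison of duration of wear. As written, section 8.8.1 tests raw levels and leaves out the one collected reading that would turn them into degradation. The bias in the difference of rises equals the difference between the two post-application means. Its size is unknown, because no fresh-film readings are given. The illustrations rest on an assumed untreated reading of 40 and assumed film readings; the rejection rates rest on treating 5.05 as the SD of raw pair differences. Under those assumptions a 5-unit gap with equal rise would almost always be declared a product difference, and reversal is possible but not certain. For durability the exposure is conditional on a drop that differs by both site and product. The plan should be changed before the data are analysed.

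**What to change.** - In section 8.8.1, add the Visit 1 post-application reading to the time points.
- Compare products within participant on the rise C_t − C_post. Pre-specify alongside it the share of film effect lost, (C_t − C_post)/(C_pre − C_post), because the rise alone depends on the initial drop. Keep raw readings as descriptive.
- Rewrite section 8.6 so that C_o, the sign and the 50% threshold match the share-lost definition, leaving one definition of degradation.
- For durability, use the elbow-minus-forearm difference in the same change measure.
- In section 8.1, state which variable 17.5 and 5.05 describe, and restate them if it is not the tested one.
- Reconcile the drying wording in the study description with the intervention description, section 4.1 and section 6.2.3.

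The cost is wording; every reading is already collected. Two downsides should be acknowledged. A change or ratio uses more than one reading, so its SD may differ from 5.05 and should be checked against the internal data; the sample size for the new variable cannot be computed from the documents. The ratio is also unstable when C_pre − C_post is small, so the plan should say in advance how such squares are handled.
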